3.10.2. Other Missing Data

Conventions for determining whether an AE is treatment emergent are discussed in Section 4.7.2. For the calculation of duration (e.g., time in years since diagnosis with hATTR) in the presence of an incomplete date, the following conventions will be used:

- Missing day: the first day of the month will be used;
- Missing day and month: duration will be calculated as the simple difference in years (e.g., year of informed consent minus year of diagnosis with hATTR);
- Missing day, month, and year: no duration will be calculated.

3.11. Visit Windows

It is expected that all visits should occur according to the protocol schedule. All data will be tabulated per the evaluation visit as recorded on the eCRF even if the assessment is outside of the visit window. In data listings, the extension study day and parent study day will be presented.

For efficacy assessments, if the scheduled 52-week or annual visits are not performed, any evaluable visit will be grouped with the 52-week or annual assessments if it is performed within 3 months of the scheduled assessment.

Unless otherwise specified above, data collected at unscheduled visits will be included in by-patient data listings and figures, but no assignment to a study visit will be made for the purpose of by-visit summary tabulations. However, unscheduled visits will be considered for baseline values, as discussed in Section 3.4, and for inclusion in any categorical shift summaries (e.g., shift from baseline to “worst” post-baseline value).

3.12. Interim Analyses

Interim analyses will be performed to support regulatory activities and publications. These analyses will be of a descriptive nature and will not involve any formal hypothesis testing.

For an interim analysis, as this study will be ongoing, a cut-off analysis approach will be implemented to ensure data quality. The interim analysis will include data on or prior to a pre-specified cut-off date. For assessments with starting/ending dates (e.g., AEs, medications, medical history), the starting date will be compared with the pre-specified cut-off date. For any assessments consisting of multiple replicates associated with a single visit, the earliest of the dates will be compared to the cut-off; if this date is on or before the cutoff date, the replicates will be included in the analysis. In particular, for mNIS+7, NIS+7, and NIS, the date for the earliest replicate of NIS-W at the visit will be compared to the cut-off date.

4. STUDY ANALYSES

4.1. Patient Disposition

Patient disposition will be tabulated and will include the following parameters: the number of patients in each analysis population, the number of patients enrolled, the number of patients treated with patisiran, the number of patients who are ongoing, the number of patients who completed the study, and the number of patients who withdrew from the study and the primary reasons for withdrawal.

A by-patient data listing of study completion information including the reason for premature study withdrawal will be presented.

4.2. Demographics and Baseline Characteristics

Demographic and baseline characteristics, baseline disease characteristics, baseline efficacy parameters, and medical history information will be summarized by study group and overall. No formal statistical comparisons will be performed.

Age, height, weight, and body mass index (BMI) will be summarized using descriptive statistics (number of patients, mean, SD, median, minimum, and maximum). Sex, race, ethnicity, and region will be summarized by presenting the numbers and percentages of patients in each category.

The following baseline disease characteristics will be summarized by presenting the numbers and percentages of patients in each category:

- Genotype (V30M vs non-V30M)
- Karnofsky Performance Status (KPS)
- Concurrent Stabilizer Use at Study Entry (yes, no)

Concurrent stabilizer use at study entry is defined as patients who were receiving TTR tetramer stabilizers (tafamidis or diflunisal) for at least 2 weeks within the first month following the first dose of patisiran in Study 006.

Time in years since diagnosis with hATTR will be summarized using descriptive statistics.

Baseline values of continuous efficacy parameters (mNIS+7, Norfolk QOL, NIS-W, mBMI, 10-meter walk test, COMPASS-31, NIS, NIS+7, grip strength, EQ-5D-5L, EQ-VAS, R-ODS, IENFD distal thigh and distal leg, and SGNFD distal thigh and distal leg) will be summarized using descriptive summary statistics. The numbers and percentages of patients in each category for baseline PND score (I, II, IIIA, IIIB, IV), baseline FAP stage (0, I, II, III), and baseline NYHA class (I, II, III, IV) will also be summarized.

All demographic and baseline data for each patient will be provided in data listings.

Medical history will be summarized by MedDRA system organ class (SOC), high level term (HLT) and preferred term (PT). A patient contributes only once to the count for a given condition (overall, by SOC, by HLT, by PT). Medical history including prior surgeries and pregnancy test results will be presented in data listings.

4.3. Pharmacokinetic Evaluations

No pharmacokinetic evaluations will be done for this study.

4.4. Pharmacodynamic Analyses

Pharmacodynamic analyses will be based on the PD analysis set.

The PD parameters include serum TTR (ELISA) and vitamin A. All summary tables and figures will be based on assessments within 21 days of last dose of patisiran. Assessments more than 21 days after last dose will be presented in listings and individual patient plots only.

Summary tables will be provided for observed values, changes and percentage changes from baseline for each scheduled time point by study group and overall. Graphical displays will be provided for the observed values of TTR and vitamin A for each scheduled time point by study group.

All PD data will be displayed in data listings.

4.5. Efficacy Analyses

Efficacy analyses will be based on the full analysis set. Summaries will be provided for each scheduled time point by study group and overall.

Neurologic impairment will be assessed by mNIS+7, NIS+7, and NIS. The observed values and changes from baseline in the composite and component scores of mNIS+7, NIS+7, and NIS will be summarized. The mNIS+7 composite score consists of the NIS weakness (NIS-W) and reflex (NIS-R) domains, quantitative sensory testing (QST) by body surface area including touch pressure (TP) and heat pain (HP), 5 nerve conduction studies ($\Sigma 5$ NCS), as well as autonomic assessment through postural blood pressure (PBP). The NIS+7 includes the NIS-W, NIS-R, NIS sensation (NIS-S), and $\Sigma 7$ Nerve tests (including sum of 5 NCS which overlaps but is not identical to the $\Sigma 5$ NCS calculated for mNIS+7 above, vibration detection threshold (VDT), and heart rate response to deep breathing [HRdb]). The total NIS score is the sum of NIS-W, NIS-R, and NIS-S. Scoring algorithms for mNIS+7, NIS+7, and NIS, including methods for handling missing components, are included in Section 7.1.

Patient reported QOL will be assessed by the Norfolk QOL-DN total score (Study 003 patients do not have to complete this assessment) and by the EQ-5D-5L index value (using U.S. references to calculate the index). Overall health will be assessed by the EQ-VAS and disability will be assessed by the R-ODS. Patient reported autonomic neuropathy symptoms will be assessed by the COMPASS-31 total score. The observed values and changes from baseline in these measures will be summarized. Continuous summaries of each Norfolk QOL-DN and COMPASS-31 domain score, as well as categorical summaries of each EQ-5D-5L domain will also be provided. Scoring algorithms for the Norfolk QOL-DN, EQ-5D-5L, R-ODS, and COMPASS-31 are included in Section 7.2, Section 7.3, Section 7.4, and Section 7.5.

Motor function assessments will include a timed 10-meter walk test and test of grip strength in the dominant arm, as well as an evaluation of ambulation using PND score and FAP stage. The observed values and changes from baseline in 10-meter walk test speed and grip strength will be summarized. Categorical summaries of FAP stage and PND score will also be provided.

Pathologic evaluation of sensory and autonomic innervation will be evaluated by IENFD analysis and quantitation of SGNFD via tandem 3 mm skin punch biopsies taken from the distal leg and distal thigh. In addition, the evaluation of dermal amyloid content (% Congo Red staining) using the same skin punch biopsy specimens analyzed for nerve fiber density (SGNFD and IENFD) will also be assessed. Continuous summaries of the observed values and changes

from baseline in IENFD, SGNFD, and dermal amyloid content will be provided by site (i.e., distal thigh, distal leg).

Nutritional status of patients will be evaluated using the mBMI, calculated as BMI (kg/m²) multiplied by albumin (g/L). The observed values and changes from baseline in mBMI will be summarized.

A categorical summary of the observed values and changes from baseline in the NYHA classification of heart failure will be provided.

Cardiac structure and function will be assessed through echocardiograms as well as measurement of serum levels of the cardiac biomarkers NTproBNP and troponin I. Descriptive statistics will be provided for actual values, changes, and percentage changes from baseline in echocardiogram parameters (including wall thickness, ejection fraction, and other echo parameters), serum levels of troponin I and NT-proBNP.

Magnetic resonance (MR) neurography data will be presented in a by-patient data listing.

4.6. Healthcare Utilization Assessments

The patient-reported pharmacoeconomics questionnaire data will be presented in a data listing.

4.7. Safety Analyses

Safety analyses will be based on the safety analysis set. All safety summaries will be presented by study group and may include an overall column as specified.

4.7.1. Study Drug Exposure

The total duration of drug exposure will be defined as (the last dose of patisiran in this study – the first dose of patisiran in this study + 21)/30.44 months. Duration of drug exposure, the total number of doses received, duration of infusion (per infusion) and amount of patisiran received (per infusion and in total) will be summarized by descriptive statistics. Summaries of the numbers and percentages of patients with at least 1 missed dose, and the number of missed doses per patient will also be provided. The total amount of drug received and the total volume infused will also be summarized. The number of patients who experienced dose interruptions for any reason will be tabulated, as well as the number of patients with dose interruptions due to an infusion related reaction (IRR).

A drug exposure table summarizing the treatment duration and interruptions under the “original” and “reduced” premedication regimens (see Section 4.7.6) will be also provided. A patient who switches from “original” to “reduced” regimen during treatment will be counted in both categories. For patients switching to the reduced regimen, the duration of exposure on the original regimen is defined as (the date of regimen change – the first dose of patisiran in this study)/30.44 months, and the duration of exposure on the reduced regimen is defined as (the last dose of patisiran in this study – the date of regimen change + 21)/30.44 months.

Dosing information for each patient will be presented in a data listing. In addition, a listing will be provided to present the durations of study drug exposure under the original regimen and reduced regimen for each patient.

4.7.2. Adverse Events

All AEs will be coded using the MedDRA coding system (version 18.0 or later) and displayed in tables and data listings using SOC and PT.

Summaries of AEs will be performed for those events that are considered treatment-emergent, where treatment-emergent is defined per protocol as any AE with onset during or after the first administration of patisiran in this study through 28 days after the last dose of patisiran. In addition, any event that was present at baseline but worsened in intensity or was subsequently considered drug-related by the Investigator through the end of the study will be considered treatment-emergent. Events with a fully or partially missing onset date will be assumed to be treatment emergent unless it can be unequivocally determined (from the partial onset date and/or a partial or complete stop date) that the event occurred prior to the first administration of patisiran. For an interim analysis where a cut-off approach is used, events with a partially missing onset date will be assumed to have started prior to the cut-off date unless it can be unequivocally determined (from the partial onset date) that the event occurred after the cut-off date; events with a fully missing onset date will be assumed to have started prior to the cut-off date.

AEs will be summarized by the number and percentage of patients reporting a given AE. A patient contributes only once to the count for a given AE (overall, by SOC, by PT). Overall event counts and frequencies may also be summarized.

An overall summary of AEs will include the numbers and percentages of patients with any AE, any AE assessed by the Investigator as related to treatment (definite or possible relationship), any severe AE, any severe AE related to treatment, any serious AE (SAE), any SAE related to treatment, any AE leading to study withdrawal, any study drug related AE leading to study withdrawal, and any deaths.

Tabulations by SOC and PT will be produced for the following: all AEs; AEs related to treatment; severe AEs; AEs leading to study withdrawal, and SAEs. Separate tables will be provided summarizing signs and symptoms of IRRs and AEs related to premedication by SOC and PT. The incidence and frequency of AEs and IRRs over time will also be summarized by SOC and PT. AEs and AEs related to treatment will also be tabulated by PT in decreasing order of frequency over all patients.

Separate tables will present AE incidence rates by maximum relationship to study drug and by maximum severity. If a patient experiences more than 1 event in a given SOC or PT, the patient is counted once for that SOC or PT according to the most related or the most severe occurrence, respectively. AEs with a missing relationship will be considered as definitely related to study drug, and AEs with a missing severity will be considered as severe.

AEs identified by the Depression and Suicide/Self-injury standardized MedDRA query (SMQ) will be summarized by PT; these AEs will be tabulated by PT in decreasing order of frequency over all patients. AEs identified by the Drug Related Hepatic Disorder SMQ will be summarized by SOC and PT. AEs identified by the Malignant or Unspecified Tumors SMQ will be summarized by HLT and PT. Other SMQs or AE groupings may be evaluated.

All AEs occurring on-study, including both treatment emergent and non-treatment emergent events, will be listed in patient data listings. A separate listing will be provided for IRRs. Listings will be provided for any AEs assessed by the Investigator as related to premedication or any study procedure. Non-treatment emergent AEs will also be listed separately.

By-patient listings will also be provided for the following: all patient deaths, all SAEs, and AEs leading to study withdrawal.

4.7.3. Laboratory Data

Clinical laboratory values will be expressed in SI units.

Summary data for each laboratory parameter will be presented for each continuous clinical laboratory parameter (including hematology, serum chemistry, coagulation studies, thyroid, and liver function tests). Descriptive statistics will be presented for the actual values, change from baseline, and percent change from baseline by scheduled visit.

For each continuous laboratory parameter, results will be categorized as low, normal, or high based on the laboratory normal ranges. Shift tables will be employed to summarize the baseline category versus the “worst” post-baseline category, where the “worst” post-baseline category will be based on the maximum difference (in absolute value) from the upper or lower limits of the normal range.

A listing will be produced for all patients with abnormal liver function tests defined as an ALT $>3 \times \text{ULN}$, AST $>3 \times \text{ULN}$, and/or total bilirubin $>2 \times \text{ULN}$ at any time point.

A table will be produced to summarize the number and percentage of patients in each of the below categories at any post-baseline time point.

- AST $>1 \ \& \ \leq 3$, $>3 \ \& \ \leq 5$, $>5 \ \& \ \leq 10$, $>10 \ \& \ \leq 20$, $>20 \times \text{ULN}$,
- ALT or AST $>1 \ \& \ \leq 3$, $>3 \ \& \ \leq 5$, $>5 \ \& \ \leq 10$, $>10 \ \& \ \leq 20$, $>20 \times \text{ULN}$,
- ALP $>1.5 \times \text{ULN}$,
- Total Bilirubin $>1.5 \ \& \ \leq 2$, $>2 \ \& \ \leq 3$, $>3 \ \& \ \leq 5$ and $>5 \times \text{ULN}$,
- Total Bilirubin $>2 \times \text{ULN}$ concurrent with ALT or AST $>3 \times \text{ULN}$.

The peak total bilirubin (at any time post-baseline) will be plotted against the peak AST or ALT level at any time post-baseline.

Laboratory test results will be graded according to the NCI CTCAE Version 4.0 or above, where applicable. A shift summary of baseline to maximum post-baseline CTCAE grade may be presented, as appropriate.

The estimated glomerular filtration rate (eGFR, mL/min/1.73 m²) will be categorized as follows: ≥ 90 ; 60-89; 30-59; 15-29 and < 15 . A shift summary of baseline to worst post-baseline eGFR category will be presented.

All laboratory data will be provided in data listings. Laboratory values outside of the normal ranges will additionally be listed separately.

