4.7.6. Premedications

All patients will receive premedication prior to the dose of patisiran in order to reduce the potential of an IRR. The original premedication regimen as outlined below was used at the start of the study. A subset of patients experienced AEs suspected to be related to steroids (e.g., flushing) and were transitioned to a reduced premedication regimen, with a reduced dose of corticosteroid to mitigate these events, as sanctioned in the protocol. After observing that the subset of patients tolerated the lower corticosteroid dose with no increase in IRRs, the protocol was amended (Amendment 1.0) to transition the rest of the patients to the reduced premedication regimen (see below).

The following original premedication regimen was used prior to protocol amendment 1.0:

- Dexamethasone 8 mg PO or equivalent administered the evening before dosing and 20 mg PO at least 60 minutes prior to the start of the infusion of patisiran;
- Paracetamol 500 mg PO or equivalent administered the evening before dosing and at least 60 minutes prior to the start of the infusion of patisiran;
- H2 blocker PO (e.g., ranitidine 150 mg or famotidine 20 mg or equivalent other H2 blocker dose) administered the evening before dosing and at least 60 minutes prior to start of the infusion of patisiran; and
- H1 blocker PO, 10 mg cetirizine or equivalent (hydroxyzine 25 mg or fexofenadine could be substituted if patient did not tolerate cetirizine) administered the evening before dosing and at least 60 minutes prior to start of the infusion of patisiran.

The following reduced premedication regimen was instituted for all patients with protocol amendment 1.0:

- Dexamethasone 10 mg IV or equivalent, administered at least 60 minutes prior to the start of the infusion of patisiran;
- Paracetamol 500 mg PO or equivalent at least 60 minutes prior to the start of the infusion of patisiran;
- H2 blocker IV (e.g., ranitidine 50 mg, famotidine 20 mg, or equivalent other H2 blocker dose) at least 60 minutes prior to the start of the infusion of patisiran; and

- H1 blocker IV, diphenhydramine 50 mg (or equivalent other IV H1 blocker available at the study site) at least 60 minutes prior to the start of the infusion of patisiran. Hydroxyzine 25 mg PO or fexofenadine 30 or 60 mg PO or cetirizine 10 mg PO could be substituted for any patient who did not tolerate IV diphenhydramine or other IV H1 blocker.

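### The laboratory shift table keeps one direction per patient, chosen by raw distance from the normal limits, and so can undercount patients who shifted to low

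*SAP*

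**What the plan says.** SAP Section 4.7.3 (Laboratory Data) sets up the general laboratory shift table in three steps.

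- Scope and categories: "For each continuous laboratory parameter, results will be categorized as low, normal, or high", using the laboratory normal ranges. Hematology, chemistry, coagulation, thyroid and liver tests are all named as continuous parameters.
- Form: "Shift tables will be employed to summarize the baseline category versus the “worst” post-baseline category". Each patient has one cell per parameter.
- Choice of the worst value: the "maximum difference (in absolute value) from the upper or lower limits of the normal range". The difference is not scaled to the limit or to the width of the range, and there is no separate rule for each direction.

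Section 3.11 (Visit Windows) adds that unscheduled visits are considered "for inclusion in any categorical shift summaries (e.g., shift from baseline to “worst” post-baseline value".

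The same section also provides for by-visit descriptive statistics, a liver table in multiples of ULN, an eGFR category shift, a separate listing ("Laboratory values outside of the normal ranges will additionally be listed separately") and CTCAE grading where applicable. The summary of those grades is discretionary: "A shift summary of baseline to maximum post-baseline CTCAE grade may be presented, as appropriate".

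**The concern.** Many of these parameters matter in both directions. A count or concentration that is too low and one that is too high are different safety findings, and a reader of a shift table expects to see how many patients moved to each. Under the stated rule, a patient who did both is shown once, and the other excursion drops out of the table.

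The choice between the two is not neutral. It compares raw distances on a scale that has a floor at zero and no ceiling, so highs can outrank lows without limit while lows cannot do the same to highs. A patient who was high at baseline, later went higher still and also had a marked low would be shown as high to high, which reads as no shift.

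Long-term safety is one of the two aims in Section 1.1.2. Section 3.2 makes all summaries descriptive, so the tables themselves carry the safety evidence.

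**Working it through.** The SAP states no figure on this point, so there is none to reproduce. The check applies the rule as written.

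**Inputs.** The categories, the single cell and the raw-distance rule come from Section 4.7.3. The SAP gives no normal ranges, so all ranges and patient values below are assumptions for illustration. L is the lower and U the upper normal limit.

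**Step 1: what the rule compares.** For a low value x < L, the distance outside the range is L - x. For a high value x > U, it is x - U. If the rule is instead read as the larger of the distances to the two limits, these become (U - L) + (L - x) and (U - L) + (x - U). The term U - L is common to both, so the ranking of a low against a high is the same.

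**Step 2: the asymmetry.** For x ≥ 0, L - x ≤ L, whereas x - U has no upper bound. Hence any x > U + L gives x - U > L, which beats every possible low value, including zero.

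**Step 3: illustrations, each patient having both values.**

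| Parameter (assumed range) | Low value: L - x | High value: x - U | Shown as | U + L (× ULN) |
|---|---|---|---|---|
| Neutrophils 1.8-7.5 | 0.4: 1.4 | 9.5: 2.0 | high | 9.3 (1.24) |
| Platelets 150-400 | 50: 100 | 505: 105 | high | 550 (1.38) |
| Glucose 3.9-5.6 | 2.2: 1.7 | 8.0: 2.4 | high | 9.5 (1.70) |
| Glucose 3.9-6.1 | 2.2: 1.7 | 8.0: 1.9 | high | 10.0 (1.64) |
| Potassium 3.5-5.0 | 2.6: 0.9 | 6.0: 1.0 | high | 8.5 (1.70) |
| White cells 4-11 | 1.5: 2.5 | 14: 3.0 | high | 15 (1.36) |

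Relative to the limit crossed, the low is the more extreme value in every row. For platelets it is 100/150 = 67% below L against 105/400 = 26% above U. For glucose with the narrower range the two are nearly equal (44% and 43%).

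The threshold moves little with the assumed range: a lower neutrophil limit of 2.0 instead of 1.8 gives 7.5 + 2.0 = 9.5 instead of 9.3.

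**Step 4: the reverse case.** With glucose 3.9-6.1 and values 2.2 and 7.0, the distances are 1.7 and 0.9, so the patient is shown as low and the high is lost. A high between U and U + L can be displaced by a deep enough low, so the loss is not only in one direction.

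**Step 5: does another committed table supply the count?**

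- By-visit statistics include the minimum and maximum (Section 3.2). They show an extreme value at a scheduled visit but not how many patients were low, and by-visit summaries generally exclude unscheduled values (Section 3.11).
- The liver table counts high values only, and the eGFR shift has its own direction. Neither is affected, and neither covers the other parameters.
- The out-of-range listing shows every such value by patient, without counts by study group.
- The CTCAE shift is optional, and its maximum grade is not separated by direction.

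No committed table gives the number of patients who shifted to low.

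**The case against.** The strongest reply is that little is lost. A patient out of range in one direction only is classified correctly. The rule matters only when one patient has both a low and a high value of the same parameter, and nothing in the SAP says how often that happens. The low value remains in the out-of-range listing, it can be seen as a visit minimum, and a low reported as an adverse event enters the tables of Section 4.7.2. Liver tests and eGFR have their own summaries, and no hypothesis test is involved. All of this stands, and it limits the size of the point. It does not supply the missing count, which is what a shift table is for.

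Two stronger readings are tempting, and the SAP does not support either.

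- A reader might infer that steroid premedication makes transient highs in neutrophils and glucose likely, and so makes masking common. Section 4.7.6 does specify "Dexamethasone 10 mg IV or equivalent, administered at least 60 minutes prior to the start of the infusion of patisiran". It does not say that this raises either parameter, and the SAP does not say when laboratory samples are taken relative to premedication.
- A reader might also infer that, over years of dosing, one high fixes a patient's category. Section 1.2.1 places clinic safety evaluations at 26 and 52 weeks and yearly thereafter, with home infusions allowed, and the SAP shows no laboratory sampling at each infusion. Unscheduled values can add to the total, but no frequency is given. By Steps 2 and 4, only a high above ULN + LLN is beyond displacement by a low.

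**Conclusion.** The point holds as a defect in how a committed safety table is built. For a patient with both a low and a high value of one parameter, the single-category rule discards one direction, and the unscaled distance favours keeping the high. The table can therefore undercount shifts to low and, less often, shifts to high.

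The algebra needs only non-negative measurements. The numerical thresholds, about 1.24 to 1.70 times ULN in the examples, rest on assumed normal ranges. The number of patients affected is unknown, so an undercount is possible but not demonstrated. The data are not lost: what is missing is a patient count by direction. In a descriptive study the consequence is modest, but the remedy is cheap enough that it should be made.

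**What to change.** In Section 4.7.3, for parameters with a meaningful lower and upper limit, replace the single worst-category shift with two shifts: baseline category to lowest post-baseline category, and baseline category to highest post-baseline category. State that a patient with both excursions is counted in both. Each patient in the Step 3 table would then count once as low and once as high.

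Where CTCAE grades exist by direction for a parameter, commit to the shift from baseline to maximum post-baseline grade and present it by direction. Grading where applicable is already planned, so this turns an optional summary into a fixed one.

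The liver table and the eGFR shift need no change. The cost is SAP wording and one extra table panel per parameter, plus the grade shift output. No new data or visits are needed.
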